18.7 B. *How long will the specimens be stored?*

Response:

18.8 B. *Who will have access to the specimens?*

Response:

18.9 B. *Who is responsible for receipt or transmission of the specimens?*

Response:

18.10 B. How will the specimens be transported?

Response:

19.0 Provisions to Monitor the Data to Ensure the Safety of Subjects

- N/A:** This study is not enrolling subjects, or is limited to records review procedures only. This section does not apply.

NOTE: *Minimal risk studies may be required to monitor subject safety if the research procedures include procedures that present unique risks to subjects that require monitoring. Some examples include: exercising to exertion, or instruments that elicit suicidality or substance abuse behavior. In such cases, N/A is not an acceptable response.*

19.1 Describe the plan to periodically evaluate the data collected regarding both harms and benefits to determine whether subjects remain safe.

Response:

The medical monitor person will periodically evaluate the collected data to assure patient's safety and well-being. A full periodontal exam will be performed at each evaluation visit to insure the overall maintenance of oral health throughout the study. Oral hygiene will be evaluated each visit. Patients will be closely monitored, as they will be seen for follow-up at day 1 and 2 weeks post-surgically. Patient's post-operative condition will be assessed according to a pre-set checklist to assure patient's safety. Suture removal will be done 2 weeks following the surgery and then evaluations and measurements at 6 weeks, 3, 6, 12, 18, and 24 months after the surgery. At the 2 weeks, 6 weeks, 6, 12, 18, and 24 months follow-ups full mouth prophylaxis will be performed. Pain index and healing index will be recorded and if patients developed any treatment complications, they are instructed to call the research staff for an additional evaluation and treatment if needed. If any other medical or dental treatment is needed, the patients will be referred to appropriate specialties.

19.2 Describe what data are reviewed, including safety data, untoward events, and efficacy data.

Response:

Updated medical and dental history, plaque index, patient's condition checklist, gingival index, recession depth, percentage root coverage, probing depth, clinical attachment level, width of keratinized tissues, gingival thickness, pain index, and healing index.

19.3 Describe any safety endpoints.

Response:

Maintenance of the overall oral health.

19.4 Describe how the safety information will be collected (e.g., with case report forms, at study visits, by telephone calls with participants).

Response:

Clinical measurements will be collected during the study visit at 6 weeks, 3, 6, 12, 18, and 24 months post-surgical treatment, healing and patient's condition will be assessed at day 1 and 2 weeks post-surgically. The medical monitor will assure patient's safety is maintained upon evaluation of all measurements. If patients developed any treatment complications, they will be informed and treated accordingly.

19.5 Describe the frequency of safety data collection.

Response:

All outcomes will be recorded at 6 weeks, 3, 6, 12, 18, and 24 months after the surgery. Healing index and patient's condition checklist at day 1 and 2 weeks post-surgically, and pain index the first 3 weeks after the surgery. Surgical time for each surgical procedure and suturing time for CTG will be calculated at the surgical visit.

19.6 Describe who will review the safety data.

Response:

Medical monitor is assigned by the organization sponsor to review the data periodically and make sure all patients are still eligible for treatment and that all the study criteria are met. The medical monitor is a certified dentist who is not involved in the patient treatment.

19.7 Describe the frequency or periodicity of review of cumulative safety data.

Response:

Monthly.

19.8 Describe the statistical tests for analyzing the safety data to determine whether harm is occurring.

Response:

Pre and post comparison through paired t-test of the measurements

19.9 Describe any conditions that trigger an immediate suspension of the research.

Response:

Developing diabetes, pregnancy, periodontal disease, immune deficiency, smoking, uncontrolled medical condition, or persistent non-compliance with study

appointments, instructions or oral hygiene instructions will result in immediate suspension from the study.

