
The following measurements will be recorded at baseline, 6 weeks, 3, 6, 12, 18, and 24 months post-surgically:

- I. Complete root coverage (CRC): The number of sites that resulted in 100% root coverage.
- II. Recession Depth (RD): Measured in millimeters from the gingival margin at the mid-buccal aspect of the root, to the CEJ or relative CEJ.

- III. Percentage root coverage (%RC): calculated as $([RD \text{ preoperative} - RD \text{ postoperative}] / RD \text{ preoperative}) \times 100\%$.
- IV. Recession classification: The recession type will be classified according to the criteria suggested by Miller
- V. Probing depth (PD): Measured in millimeters from the gingival margin to the base of the periodontal sulcus at 6 sites per tooth.
- VI. Clinical attachment level (CAL): Measured in millimeters from CEJ or relative CEJ to the base of the periodontal sulcus at 6 sites per tooth.
- VII. Width of the keratinized tissue (KTW): Measured in millimeters at mid-buccal aspect of the tooth from the gingival margin to the mucogingival junction.
- VIII. Gingival Thickness: Measured in millimeters at the mid-buccal of the gingiva and 2 mm apical the gingival margin at the attached gingiva or the alveolar mucosa using a #15 endodontic reamer with a silicon disk stop.
- IX. Plaque index (PI): Is used for estimating the status of oral hygiene by measuring dental plaque that occurs in the areas adjacent to the gingival margin.
- X. Gingival index (GI): GI is measured according to Loe and Sillness and scored on a scale of 0 to 3.

More measurements include:

- ❖ Healing index (HI): A horizontal scale from 1-5 evaluating tissue color, response to palpation, granulation tissue, incision margin, suppuration, adopted from Aleksic²⁵. To be assessed at day 1 and 2 weeks post-surgically as follows:
 - 1 (very poor)= $\geq 50\%$ of the gingiva is red, bleeding on palpation, presence of granulation tissues, incision margin not epithelialized (loss of epithelium beyond incision margin), and presence of suppuration.
 - 2 (poor)= $\geq 50\%$ of the gingiva is red, bleeding on palpation, presence of granulation tissues, incision line not epithelialized (connective tissue exposed), and no suppuration.
 - 3 (good)= 25-50% of the gingiva is red, no bleeding on palpation, no granulation tissues, no connective tissue exposed, and no suppuration.

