 - 4 (very good)= $< 25\%$ of the gingiva is red, no bleeding on palpation, no granulation tissues, no connective tissue exposed, and no suppuration.

- 5 (excellent)= all tissues are pink, no bleeding on palpation, no granulation tissues, no connective tissue exposed, and no suppuration.
- ❖ Pain index (PN): Pain is recorded on a horizontal pain scale of 0-10, Pain index to be recorded by the patients at 9 am, 3pm, and 9 pm from the day of the surgery and for 3 weeks post-treatment. Also, the patients will be asked to record the name of pain medications taken, dosage, and frequency for the 3 weeks after the surgery. Pain index as follows; Mild for “0 to 3,” moderate for “4 to 6,” and severe for “7 to 10.” None to minimal pain meant little or no discomfort; moderate was any pain that bothers the patient and mildly affects normal daily functions and activities; and severe is considered any pain that could not be tolerated and even disrupts the patient’s daily functions or activities ²⁶.
- ❖ Patient’s Condition Checklist: the patient’s condition will be assessed Patient’s Condition Checklist: the patient’s condition will be assessed according to a pre-set checklist at day 1 and 2 weeks post-surgically, as follows:
 - Clinical appearance of the face: Swelling: severity (mild, moderate, severe), location, lymph nodes, hard or fluctuant, hot or normal temperature; coloration.
 - Bleeding: if yes, location, nature (persistent, intermittent, stops with pressure).
 - Infection or sloughing: if yes, location, extent in mm vertically and horizontally, probable cause of infection.
 - Patient temperature.
 - Pain medications taken: name, dosage, quantity.
 - Photos will be taken.
- ❖ Time: surgical time will be calculated for each surgical procedure from the time of surgical incision or pinhole creation to the conclusion of the surgery; also the time of suturing will be calculated for CTG.

10.2 Describe what data will be collected.

NOTE: For studies with multiple data collection points or long-term follow up, consider the addition of a schedule or table in your response.

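### The only statistical test named for detecting harm, a pre/post paired t-test, does not fit the acute harm data and can mask worsened sites on recession depth

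*Protocol*

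**What the plan says.** Item 19.8 of the protocol puts the question "Describe the statistical tests for analyzing the safety data to determine whether harm is occurring". The whole answer is "Pre and post comparison through paired t-test of the measurements". It names no measure, time point, direction, threshold or comparison between techniques.

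Item 19.2 lists the data reviewed for safety: "Updated medical and dental history, plaque index, patient's condition checklist, gingival index, recession depth, percentage root coverage, probing depth, clinical attachment level", then keratinized tissue width, gingival thickness, pain index and healing index. Item 19.3 gives the safety endpoint as "Maintenance of the overall oral health".

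Section 10.1 sets the timing. Ten items, among them recession depth, root coverage, probing depth, attachment level, plaque index and gingival index, fall under "The following measurements will be recorded at baseline, 6 weeks, 3, 6, 12, 18, and 24 months post-surgically". The Healing Index is "To be assessed at day 1 and 2 weeks post-surgically as follows". The condition checklist (swelling, bleeding, infection or sloughing) has the same two time points. The Pain Index runs "from the day of the surgery and for 3 weeks post-treatment".

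Sections 19.1, 19.6 and 19.7 add a medical monitor who is not involved in treatment and a monthly review of cumulative safety data.

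**The concern.** A pre/post test needs a value before surgery. Section 21.1 lists pain, bleeding, swelling, bruising, infection, numbness and failure of the procedure among the foreseeable risks. Most of the acute ones are captured by the three instruments that start at or after surgery. Section 19 therefore names these instruments as safety data and then names a test that does not fit them.

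Where a baseline does exist, the question changes. Both operations are done to reduce recession, so a significant pre/post change in recession depth says that the operation worked on average. It does not say that no site was damaged. In a split-mouth trial the informative safety question is whether one technique harms more than the other in the same mouth, and a pre/post test does not ask it. At stake is that a significant result could be reported as evidence of safety when it is evidence of mean benefit.

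**Working it through.** **1. Which safety data have a pre-surgical value (section 10.1)**

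| Data in 19.2 | Baseline scheduled? | What a pre/post t-test would show |
|---|---|---|
| Healing Index (ordinal, 1-5) | No: day 1 and 2 weeks | Not computable |
| Condition checklist (mostly categorical) | No: day 1 and 2 weeks | Not computable |
| Pain Index (0-10) | None defined | No defined pre value |
| Recession depth, % root coverage | Yes (% root coverage is 0 at baseline by its formula) | Intended benefit |
| Attachment level, keratinized tissue width, gingival thickness | Yes | Plausibly intended benefit |
| Plaque index, gingival index, probing depth | Yes | Mean worsening, if large enough |

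A 9 am pain entry on the day of surgery might precede the operation, but the protocol does not define it as a baseline.

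**2. The plan's own figure**

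Item 19.8 states no number. The sample size in 17.1 fixes the n used below. Inputs: SDs 0.91 and 0.95, correlation 0.46, difference 0.4 mm, two-sided 0.05, power 80%.

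- SD of the paired difference = √(0.91² + 0.95² − 2 × 0.46 × 0.91 × 0.95) = 0.967.
- A paired t-test (noncentral t) needs n = 48, with power 80.1%. The stated 48 (52 with 4 dropouts) is reproduced.

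**3. Illustration on recession depth**

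Assumed, not in the protocol: of 52 sites treated with one technique, 47 gain 2 mm and 5 lose 1 mm. Noise SD is 0.91 mm, borrowed from 17.1.

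- Mean gain = (47 × 2 − 5 × 1)/52 = 89/52 = 1.71 mm.
- SD of the mixture = 0.893 (variance 0.798). Adding 0.91² = 0.828 gives a total variance of 1.626.
- t = 1.71/(√1.626/√52) = 9.7, p < 0.001 in the direction of benefit.
- Worsened sites: 5/52 = 9.6%, exact 95% CI 3.2% to 21.0%.

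**4. Range at n = 48 (simulation, 20,000 runs per setting)**

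Assumed: unharmed sites gain 1.0 to 2.0 mm on average, harmed sites lose 1 mm, within-site SD 0.95 mm.

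| Sites harmed | Declares benefit | Declares harm |
|---|---|---|
| 10% | 99.6% to 100% | about 0% |
| 20% | 89% to 100% | about 0% |
| 30% | 54% to 99% | about 0% |
| 40% | 17% to 87% | at most 0.2% |

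At n = 28, the number of cases already treated according to 17.1, the test declares benefit in 68% to 100% of runs with 10% to 20% of sites harmed.

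**5. Measures with little expected gain (plaque index, gingival index, probing depth)**

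Assumed: no mean change in unharmed sites, one unit of worsening in harmed sites, SD 0.5 to 0.95, n = 48.

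- 10% of sites worsened: harm flagged in 10% to 21% of runs.
- 30% worsened: harm flagged in 49% to 86%.
- Benefit declared in at most 1.1% of runs in any setting tried (5% to 30% worsened).
- Smallest mean worsening detectable with 80% power: 0.41 SD at n = 48, 0.55 SD at n = 28.

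**6. Would a paired test of events be a better criterion?**

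If 5 subjects are harmed only at the PST site and none only at the CTG site, exact two-sided McNemar gives p = 2 × 0.5⁵ = 0.0625. A significance test is weak for rare events, so counts and intervals should carry the message.

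**The case against.** The best defence is that 19.8 answers a form question about statistical tests and is not the whole safety plan. A case of infection or sloughing reaches the medical monitor through the checklist without any t-test. Item 19.4 lists clinical measurements apart from healing and patient condition, so the measurements in 19.8 may mean only the ten items with a baseline. For an endpoint of overall oral health, a pre/post comparison of plaque, gingival index, probing depth and attachment is a natural choice. Pain and healing are also trial endpoints in section 2.1, and their comparison between techniques may be set out in an analysis plan that is not shown.

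Much of this stands, and it rules out three stronger readings:

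- **That harm is judged only by the t-test.** The monitor, the monthly review and the checklist are separate safeguards.
- **That the test will show benefit on every measure with a baseline.** Section 10.1 requires plaque and gingival indices below 15% before surgery, so they have little room to improve. Mean worsening on them, or on probing depth, would appear as worsening.
- **That monthly review means about 24 unadjusted looks at the primary endpoint.** Item 19.7 says that data are reviewed monthly. Neither it nor 19.8 says that the t-test is run monthly. A within-technique change from baseline also tests a different hypothesis from the PST-versus-CTG contrast in 17.1, and no stopping rule for benefit is attached to it. Such looks would not in themselves inflate the error rate of that contrast.

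The defence does not rescue 19.8. Even on the narrow reading, the only test named for harm leaves out pain, healing and the checklist, and on recession depth it answers a question about efficacy. The protocol states this choice itself, so it is not a detail deferred to another document.

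**Conclusion.** The concern holds in a limited form: the method stated in 19.8 does not serve its stated purpose. It does not fit three of the safety instruments in 19.2. On recession depth and root coverage it measures intended benefit and, with 10% to 20% of sites worsened by 1 mm, would declare benefit in 89% to 100% of trials at n = 48 and practically never harm. On plaque index, gingival index and probing depth it points in the right direction but misses a 10% harmed minority in roughly four of five trials or more. It compares no techniques.

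The mismatch with the schedule follows from the text alone. The sizes rest on assumed gains, losses, harmed shares and, for the indices, SDs; the protocol gives none of these. The point should be corrected, but it does not mean that subjects go unmonitored.

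**What to change.** Replace the answer in 19.8 with the following:

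- For each technique, the number and percentage of subjects, with exact 95% CI, who have: infection or sloughing; persistent bleeding; moderate or severe swelling; severe pain (7-10 on the protocol's scale); and a study site with recession depth or attachment level worse than baseline.
- The within-subject PST-minus-CTG difference in each proportion, with its 95% CI. Exact McNemar may be added as a descriptive supplement, not as the criterion for harm, because its power is low for rare events.
- These tabulations go to the monthly review.
- Pre/post means of plaque index, gingival index, probing depth and attachment level may stay as descriptive summaries of overall oral health.

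The cost is a change of wording and slightly more tabulation. The items are already collected, the severity categories already stand in section 10.1, and no visit or treatment changes.

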17.0 Data Management and Analysis

17.1 *Describe the data analysis plan, including any statistical procedures. This section applies to both quantitative and qualitative analysis.*

Response: The main aim of this study is to assess the efficacy of the pinhole surgical technique in treating gingival recession compared to an established surgical treatment method. We therefore will focus in this clinical trial on one primary endpoint, namely recession depth. The change in recession depth during the study observation period will therefore be used for the calculation of sample size.

We previously have calculated the sample size based on parameter estimates gathered from published studies. We now have recalculated the sample size and used parameters estimates generated from 28 cases already treated in this clinical trial. This should give more accurate parameters to calculate the sample size needed. We also used the 80% power. Accordingly, we used the following assumptions to calculate the sample size:

Standard deviation in the group A: 0.91

Standard deviation in the group B: 0.95

Correlation: 0.46

Effect size (the difference in the reduction in recession depth between the test and control groups): 0.4 mm

Level of significance: 0.05

Power: 80%

Type of test: 2-sided

Based on these assumptions, the sample size is 48. In addition, we anticipate a drop out of 4 subjects. Hence, the total number of participants needed for this study is 52.

17.2 *If applicable, provide a power analysis.*

NOTE: This may not apply to certain types of studies, including chart/records reviews, survey studies, or observational studies. This question is asked to elicit whether the investigator has an adequate sample size to achieve the study objectives and justify a conclusion.

Response: Please see item 17.1

17.3 *Describe any procedures that will be used for quality control of collected data.*

Response:

Standardization of measurement and radiographs and assurance of intraoperator reproducibility will be performed.

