20.0 Withdrawal of Subjects

- N/A: This study is not enrolling subjects. This section does not apply.

20.1 Describe **anticipated** circumstances under which subjects may be withdrawn from the research without their consent.

Response:

Lack of compliance with oral hygiene, post-operative instructions, or follow-up appointments. Also, if any changes occurred in the medical history or medications taken that might affect the treatment, healing, or outcomes e.g. some blood pressure or epilepsy medications, pregnancy, antibiotics, diabetes, smoking. Lastly, if any other oral condition occurred on the teeth of interest e.g. cavity, root canal, loosening of the teeth or pockets. All subjects will be informed of any new information that may affect their health, welfare, or choice to stay in the research.

20.2 Describe any procedures for orderly termination.

NOTE: Examples may include return of study drug, exit interview with clinician. Include whether additional follow up is recommended for safety reasons for physical or emotional health.

Response:

At the end of the study, the patients will be given a report of the study and the results, and they will be informed if any further procedure is needed for the site maintenance and the future recommendations will be explained.

20.3 Describe procedures that will be followed when subjects withdraw from the research, including retention of already collected data, and partial withdrawal from procedures with continued data collection, as applicable.

Response:

Upon withdrawal from the study before the one-month follow-up after the surgery, all measurements and data collected will be discarded and will not be used in any research publication. If withdrawal occurred after the 6 weeks follow-up, the patient will be asked if they would agree on using their data in the study analysis and publication. If they agreed, data will be retained, and if not will be discarded.

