21.0 Risks to Subjects

21.1 List the reasonably foreseeable risks, discomforts, hazards, or inconveniences to the subjects related to their participation in the research. Consider physical, psychological, social, legal, and economic risks. Include a description of the probability, magnitude, duration, and reversibility of the risks.

NOTE: Breach of confidentiality is always a risk for identifiable subject data.

Response:

Some forms of gingival recession will benefit from soft tissue graft procedure and will be recommended to be done for the subjects whether they are in a study or not as standard of care. All soft tissue grafting surgeries might possess the same surgical risks including; pain, discomfort, bleeding, failure and redo of procedure, swelling, bruising, infection, tooth sensitivity, temporary or permanent numbness in surgical area, inflammation.

Risks related to the anesthetics might include but are not limited to allergic reactions, accidental swallowing of foreign matter, facial swelling or bruising, pain, soreness or discoloration at the site of injection of the anesthetics.

Finally, Breach of confidentiality is always a risk for identifiable subject data.

21.2 Describe procedures performed to lessen the probability or magnitude of risks, including procedures being performed to monitor subjects for safety.

Response:

Review of medical history and medications of the patient, patients will be instructed to use over the counter pain medications including ibuprofen and/or acetaminophen as needed. Also, maintenance of good oral hygiene will decrease the chance of infection or inflammation of the surgical site. Day one and 2 weeks follow-up will be performed and a patient's condition checklist will be followed. Also, the patients will record their pain throughout the first 3 weeks after the surgery.

*21.3 If applicable, indicate **which procedures** may have risks to the subjects that are currently unforeseeable.*

Response:

All soft tissue surgeries will have similar risks whether in the study or outside the study.

21.4 If applicable, indicate which research procedures may have risks to an embryo or fetus should the subject be or become pregnant.

Response:

Upon pregnancy the subject will be withdrawn from the study.

21.5 If applicable, describe risks to others who are not subjects.

Response:

None

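### Sections 19.9 and 21.4 take subjects out for whole-person events even after both sites are operated on, with no provision to keep measuring the pair; the 4-subject allowance must absorb this and has no stated basis

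*Protocol*

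**What the plan says.** Protocol 19.9 names the triggering events, "Developing diabetes, pregnancy, periodontal disease, immune deficiency, smoking, uncontrolled medical condition, or persistent non-compliance with study", and continues that "appointments, instructions or oral hygiene instructions will result in immediate suspension from the study". No time limit is given, and nothing depends on whether one or both sites have been operated on. Section 21.4 is equally firm: "Upon pregnancy the subject will be withdrawn from the study".

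Section 20.1 covers much of the same ground (non-compliance, pregnancy, diabetes, smoking) and adds antibiotics and other changes: "if any changes occurred in the medical history or medications taken that might affect the treatment, healing, or outcomes". It answers a question about when subjects might be withdrawn without their consent, so its grounds read as discretionary.

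Section 20.3 says what happens to the data. On withdrawal before one month, everything is discarded. After the 6-week visit, data are kept if the subject agrees. The template question also asks about continued data collection after partial withdrawal; the response offers none.

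Section 10.1 puts the second surgery 3 weeks after the first and schedules measurements at 6 weeks and at 3, 6, 12, 18 and 24 months. Section 17.1 sizes the trial on recession depth: "We therefore will focus in this clinical trial on one primary endpoint, namely recession depth". It needs 48 subjects and adds 4: "In addition, we anticipate a drop out of 4 subjects".

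**The concern.** Study surgery ends at the second operation. From then on the subject contributes measurements at two sites that have already been randomised and treated. A whole-person event such as diabetes, pregnancy or smoking occurs in one mouth holding both sites. Stopping measurement at that point spares the subject no study operation, but it ends the series of paired recession depths on which the trial is sized.

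This is settled by the protocol. An analysis plan can say how missing values are handled, but it cannot recover visits that the protocol stopped.

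Two things are at stake. One is precision, because the sample size leaves room for only 4 losses from all causes. The other is whom the later results describe, since the later visits would tend to show subjects who stayed healthy and compliant. The point concerns whole-person events only. Periodontal disease, also on the 19.9 list, and the tooth-level conditions in 20.1 can affect one site alone and are set aside here.

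**Working it through.** **Timing.** Of roughly 104 weeks of follow-up, 3 fall between the surgeries, so about 97% (101/104) of the time at risk comes after both sites are treated. The earliest post-operative measurement of the first site, at 6 weeks, is already 3 weeks after the second surgery. Every scheduled post-operative recession depth is therefore taken after both operations.

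**Inputs (Protocol 17.1).** "Standard deviation in the group A: 0.91"; "Standard deviation in the group B: 0.95"; correlation 0.46; difference 0.4 mm; two-sided 5% level; 80% power; 48 subjects plus 4, giving 52.

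**Reproducing the plan's figure.**

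- SD of the paired difference = √(0.91² + 0.95² − 2 × 0.46 × 0.91 × 0.95) = √(0.8281 + 0.9025 − 0.7953) = 0.967 mm.
- The normal approximation, ((1.960 + 0.842) × 0.967 / 0.4)², gives 45.9, or 46 pairs.
- The paired t-test with the noncentral t distribution gives 48 pairs, with power 80.1%. This matches the protocol exactly.

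**Size of the allowance.** 4/52 = 7.7% in total. If the analysis is at 24 months, the annual equivalent is 1 − √(48/52) = 3.9%. If it is at 12 months, it is 7.7% a year.

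**Power by pairs with the outcome (noncentral t).**

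| Pairs | 52 | 48 | 47 | 46 | 44 | 42 |
|---|---|---|---|---|---|---|
| Power | 83.3% | 80.1% | 79.3% | 78.4% | 76.5% | 74.5% |

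**Chance of exceeding the allowance.** The documents give no rate for any of these events or for ordinary drop-out, so the total loss rates below are assumptions. The chance is the binomial probability of 5 or more losses among 52. Pairs left are 52 × (1 − rate), rounded. Enrolment needed to keep 48 pairs is 48 / (1 − rate), rounded up.

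| Assumed total loss | Chance of more than 4 lost | Pairs left | Power at that number | Enrolment to keep 48 |
|---|---|---|---|---|
| 2% | 0.4% | 51 | 82.6% | 49 |
| 5% | 12% | 49 | 81.0% | 51 |
| 7.7% | 37% | 48 | 80.1% | 52 |
| 10% | 60% | 47 | 79.3% | 54 |
| 15% | 91% | 44 | 76.5% | 57 |
| 20% | 99% | 42 | 74.5% | 60 |

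**The sections side by side.** For diabetes, pregnancy, smoking and non-compliance, 19.9 is automatic and 20.1 is discretionary. For pregnancy, 21.4 is automatic. Suspension in 19.9 is not defined, and nothing says whether it differs from the withdrawal that 20.3 regulates. Section 20.3 also leaves the interval between one month and 6 weeks uncovered.

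**The case against.** The strongest reply is that little may be lost. Most such events would arise after the 6-week visit, and 20.3 then keeps earlier data if the subject agrees. Section 17.1 refers to change over the observation period without naming a visit, and 11.2 gives participation as 12 to 24 months. An analysis at 12 months, or one using all available visits, would lose less. This stands. A reader might infer that every removal deletes a pair from the primary analysis; the documents do not support that. What is certain is the loss of later visits, and the pair is lost only for an analysis at a time point after removal.

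A reader might also infer that the allowance will easily be exceeded. That is not shown. At an assumed 2% to 5% total loss it usually holds, and a small overshoot costs about one power point per lost pair. The rates also combine forced removals with ordinary drop-out, so no share can be assigned to 19.9.

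Nor can one say that the removals serve no purpose. They mirror the entry exclusions in 6.2. An event shared by both sites need not affect a graft and a membrane technique equally. Because 1.2 states a non-inferiority hypothesis, values taken after smoking or non-compliance could narrow a real difference and favour the test technique. This is a good reason to report results both with and without such values. It is not a reason to leave them unmeasured.

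Finally, medication changes and antibiotics appear only in 20.1, as discretionary grounds, and should not be read into 19.9. Follow-up visits also include procedures such as thickness measurement with a reamer and prophylaxis, so whether a given procedure suits a given person is a clinical matter.

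**Conclusion.** The point holds in a limited form. As written, 19.9 and 21.4 end participation automatically for whole-person events, without a time limit and regardless of whether both sites are treated. They disagree in force with 20.1, and 20.3 provides for no continued measurement. Following the plan therefore loses later paired recession depths that could have been collected.

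The sample size is correct on its inputs (48 pairs, 80.1%) and has no reserve beyond 4 losses. No basis is given for the 4, and they must cover these removals as well as ordinary drop-out. The likely cost is modest: 79.3% power at 47 pairs and 74.5% at 42, if those are the pairs available at the analysis visit. Whether the allowance is exceeded depends on a loss rate that the documents do not give; the break-even is 7.7% in total. The expected harm is to precision and completeness. No bias in a particular direction is claimed. This should be amended, but it does not invalidate the design.

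**What to change.** 1. Reconcile 19.9, 20.1 and 21.4 so that the same event has the same consequence throughout, and define suspension in relation to withdrawal. Which clinical rule applies is for the investigators to decide.
2. Separate the end of study procedures from the end of data collection. State in 20.3 that, once both sites have been operated on and with the subject's agreement, recession depth continues to be measured at both sites on schedule after such an event, and that the event and its date are recorded. Which visit procedures suit that person remains a clinical decision.
3. Analyse recession depth with and without the post-event values and report both.
4. In 17.1, say what the allowance of 4 covers and the loss rate it assumes, or restate the power for the pairs expected to remain.

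The cost is one amendment and a few further visits, with no additional subjects for the data-collection change. The small downside is that some values will be measured after such an event, which the paired reporting in item 3 makes visible.
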